6.11. Investigator's Final Report

Upon completion of the study, the investigator, where applicable, will inform the institution; the investigator or institution will provide the IRB with a summary of the study's outcome and the sponsor and regulatory authority(ies) with any required reports.

6.12. Records Retention

The investigator agrees to keep the records stipulated in Section 6.8.1 and those documents that include (but are not limited to) the study-specific documents, identification log of all participating subjects, medical records, source worksheets, all original signed and dated ICFs, copies of all eCRFs, query responses, and detailed records of drug disposition, to enable evaluations or audits from regulatory authorities, the sponsor, or its designees. Furthermore, ICH 4.9.5 requires the investigator to retain essential documents specified in ICH E6 (Section 8) until at least 2 years after the approval of a marketing application for a specified drug indication being investigated or, if an application is not approved, until at least 2 years after the investigation is discontinued and regulatory authorities are notified. In addition, ICH 4.9.5 states that the study records will be retained until an amount of time specified by applicable regulatory requirements or for a time specified in the clinical study site agreement between the investigator and sponsor.

Refer to the clinical study site agreement for the sponsor's requirements on record retention. The investigator will contact and receive written approval from the sponsor before disposing of any such documents.

6.13. Publications

The sponsor may publish any data and information from the study (including data and information generated by the investigator) without the consent of the investigator.

Manuscript authorship for any peer-reviewed publication will appropriately reflect contributions to the production and review of the document. Publication of study results will be in-line with the agreement executed by and the sponsor for the conduct of the study.

7. Study Management

7.1. Monitoring

7.1.1. Monitoring of the Study

Study site monitoring visits will be performed by the sponsor or designee periodically during the study to ensure that all aspects of the protocol are followed. Source documents will be reviewed for verification of data recorded in the eCRFs. Additionally, all aspects of the study and its documentation will be subject to review, including but not limited to, the investigator's binder, study drug, subject medical records, informed consent documentation, eCRFs, and associated source documents. It is important that the investigator and other study personnel are available during the monitoring visits and that sufficient time is devoted to the process.

7.1.2. Inspection of Records

The investigator involved in the study will permit study-related monitoring, audits, IRB review, and regulatory inspection(s). In the event of an audit, the investigator agrees to allow the sponsor, representatives of the sponsor, the competent authority, or other regulatory agency access to all study records. The investigator will promptly notify the sponsor of any audits scheduled by any regulatory authorities and promptly forward copies of any audit reports received to the sponsor.

7.2. Management of Protocol Amendments and Deviations

7.2.1. Modification of the Protocol

Any changes in this research activity, except those necessary to remove an apparent, immediate hazard to a subject, must be reviewed and approved by the sponsor or designee. Amendments to the protocol must be submitted in writing to the investigator's or subinvestigator's IRB for approval before subjects can be enrolled into an amended protocol.

7.2.2. Protocol Deviations

The investigator will conduct the study in compliance with the protocol agreed to by the sponsor and, if required, by the regulatory authority and that was given approval/favorable opinion by the IRB.

The investigator, or designee, will document and explain any deviation from the approved protocol.

The investigator will notify the IRB of any deviations from the protocol in accordance with local procedures.

7.3. Study Termination

The study will be completed as planned unless the following criteria are satisfied that require early termination of the study:

- 1. New information regarding the safety or efficacy of the study drug that indicates a change in the known risk/benefit profile for the investigational product, such that the risk/benefit is no longer acceptable for subjects participating in the study.
- 2. Significant violation of GCP that compromises the ability to achieve the primary study objectives or compromises subject safety.

The sponsor reserves the right to suspend or terminate the study at any time.

[figure not shown]
The study site may be terminated if the site (including the investigator) is found in significant violation of GCP, protocol, or contractual agreement, or is unable to ensure adequate performance of the study.

7.4. Final Report

Whether the study is completed or prematurely terminated, the sponsor's designee will ensure preparation of the clinical study report and provision of it to the regulatory agency(ies) as required by the applicable regulatory requirement(s). The clinical study report will be structured in accordance with the FDA guideline document entitled, "ICH E3 Structure and Content of Clinical Study Reports" (DHHS 1996).

8. Appendices

8.4. Appendix D: Pharmacokinetic, Pharmacodynamic, and Meal Time Points – Part 2

8.5. Appendix E: Responsibilities of the Investigator

Clinical research studies sponsored by the sponsor are subject to the regulations of the FDA. The responsibilities imposed on the investigator by the FDA are summarized in the "Statement of Investigator" (Form FDA 1572), which must be completed and signed before the investigator may participate in this study.

In signing a Form FDA 1572, the investigator agrees to assume the following responsibilities:

- 1. Conduct the study in accordance with the protocol.
- 2. Personally conduct or supervise the staff who will assist in the conduct of the study.
- 3. Ensure that all colleagues and employees assisting in the conduct of the study are informed of these obligations.
- 4. Secure prior approval of the study and any changes by an appropriate IRB that conforms to FDA requirements.
- 5. Ensure that the IRB will be responsible for initial, continuing review, and approval of the protocol. Promptly report to the IRB all changes in research activity and all anticipated risks to subjects. Make at least yearly reports on the progress of the study to the IRB and issue a final report within 3 months of study completion.
- 6. Ensure that requirements for informed consent as outlined in 21 CFR Part 50 are met.
- 7. Obtain valid informed consent from each subject who participates in the study and document the date of consent in the subject's medical chart. Each ICF will contain a subject authorization section that describes the uses and disclosures of a subject's personal information (including personal health information) that will take place in connection with the study.
- 8. Prepare and maintain adequate case histories of all persons entered into the study, including eCRFs, hospital records, laboratory results, etc, and maintain this data for a minimum of 2 years after notification by the sponsor that all investigations have been discontinued or that the FDA has approved the New Drug Application. Before disposing of any records, the sponsor must be contacted.
- 9. Allow possible inspection and copying by the FDA of eCRFs and records of drug distribution.
- 10. Maintain current records of the receipt, administration, and disposition of study medication, and return all unused study medication to the sponsor.
- 11. Report adverse reactions to the sponsor promptly. In the event of an SAE, immediately notify the sponsor and medical monitor within 24 hours of knowledge of the event.

9. Reference List

## VERSION 2.0 PREPARED BY:

## 1 Abbreviations

Abbreviation	Term/Description
AUC	Area under the curve
CI	Confidence interval
CRU	Clinical research unit
ECG	Electrocardiogram
HR	Heart rate
LQT2	Long QT Syndrome Type 2
LQT3	Long QT Syndrome Type 3
LQTS	Long QT syndrome
Min	Minimum
Max	Maximum
PD	Pharmacodynamic(s)
PK	Pharmacokinetic(s)
PR	PR interval of the ECG
QRS	QRS interval of the ECG
QTc	Corrected QT interval
QTcF	Corrected QT interval using Fridericia's formula
SAP	Statistical analysis plan
SD	Standard deviation
SE	Standard error
SGK-1	Serum and glucocorticoid- regulated kinase 1
TID	Three times a day

## 2 Introduction

Section	Original Text	Amended Text	Rationale
3	This will be a Phase 2, single-blind, placebo run-in, multiple-dose safety study to evaluate the safety, tolerability, and PK of LQT-1213 in patients with LQT2 and LQT3. All patients will have a QTcF >490 and <600ms. Patients will be recruited by the sponsor using a network of cardiologists who treat LQTS patients and transported to the inpatient clinical research unit to participate in the study.	This will be a Phase 2a, single-blind, placebo run-in, multiple-dose safety study to evaluate the safety, tolerability, and PK of LQT-1213 in patients with LQT2 and LQT3. All patients will have a QTcF ≥480 and ≤560 ms. Up to 12 participants with LQT2 and up to 12 participants with LQT3 will be enrolled.	Update per Protocol v7.0.
	After initial remote screening by the clinical research unit, individual patients will undergo a 2-day, single blind run-in period followed by dosing of LQT- 1213.	After initial remote screening by the clinical research unit (CRU), individual patients will undergo a 1-day, single blind run-in period followed by 3 dosing days of LQT-1213, administered three times a day (TID) at time 0, 8, and 16 hours on Days 2 and 3, with the final dose on Day 4 at time 0, though these time points may be adjusted based upon emerging data.	
	Approximately 7 days after the end of treatment in Period 2, the Follow-up visit will be conducted remotely via telephone call. The duration of treatment for each subject in the study will be approximately 13 days, from admission on Day –2 to the telephone follow-up call. This	Approximately 7 days after discharge from the CRU, the Follow-up visit will be conducted remotely via telephone call. The duration of treatment for each subject in the study will be approximately 13 days, from admission on Day -1 to the	

Confidential Page 5 of 14

[figure not shown]
	does not include the 28-day screening period.	telephone follow-up call. This does not include the 60-day screening period.	
4	In Part 2, ECG data will be collected from Day -1 through Day 5. At each timepoint, three ECGs will be recorded and 3 beats analyzed per ECG. For analysis purpose, the average of all analyzed ECG complexes on the triplicate ECGs will be averaged in all ECG analyses. While 24-hour Holter were collected from which ECGs can be extracted, this analysis utilizes concomitantly recorded 12 lead ECGs.	In Part 2, ECG data will be collected from Day -1 through Day 5. At each time point, three (triplicate) ECGs will be recorded. For analysis purpose, the average of the triplicates ECGs will be analyzed. Additional post-hoc analyses based on all values of the triplicates were also conducted. While 24-hour Holter were collected from which ECGs can be extracted, this analysis utilizes concomitantly recorded 12 lead ECGs.	Update per Protocol v7.0.
	The timepoints for cardiodynamic ECG assessments can be found in Appendix 8 of the protocol.	The time points for cardiodynamic ECG assessments can be found in Appendix D of the protocol.	
5.1	None	New sentences were added: All ECG data will be summarized by LQT-1213 dose groups of 16 mg and 7 mg, unless otherwise specified.  Typically, the confidence intervals (CIs) shall be rounded to two decimal places greater than the precision of the original value; however, due to space constraint on the printout, as well as for easier review, the CIs were rounded (post- hoc) to one decimal place greater than the precision of the original value.	Clarification on general approach for data summaries and analyses.
6.1	Each ECG parameter will be summarized by visit. All data will be listed, including each reading and the average of all readings for each timepoint. Descriptive statistics (e.g., number of subjects, mean, SD, median, maximum and minimum) will be used to summarize the absolute values of the ECG variables and the corresponding change- from-baseline values for all subjects at each time point on each of Days 1-5. Data-based (i.e., not model-based) 2-sided 90%, 85%,	Each ECG parameter will be summarized by visit  Descriptive statistics will be used to summarize the values of the ECG variables and the corresponding changes (and percent changes) from baseline values at each time point on each of Days 1-5. The 2-sided 90%, 85%, and 80% CIs of the means will be derived based on t-test.	Clarification on general approach for data summaries and by-subject listings.

Confidential Page 6 of 14

	and 80% 2-sided CI of the mean will be summarized for the absolute and change-from-baseline data only.		
6.2	In this analysis, QTcF values at each timepoint on Day 2, 4, and 5 will be compared to the time-matched QTcF values on Day 1 (placebo) using paired t-test.	In this analysis, QTcF values at each time point on Days 2 and 4 will be compared to the time-matched QTcF values on Day 1 (placebo) using paired t-test, which is the same as analyzing the difference of the time-matched QTcF values using one-sample t-test.	Deletion of Day 5 as the time points are not the same as Day 1;  Clarification on analysis methods and correction on multiple p-values;  Addition of statistical interpretation on p-value versus multiple CIs;  Addition of new post-hoc analyses that pooled 16 mg and 7 mg dose group together.
6.3			

Confidential Page 7 of 14

6.4	
 
Key Placebo-Corrected Analyses
 
The QTcF values on Days 2, 4 and 5 during the following times, will be compared to the values on Day 1 (placebo) utilizing the trapezoidal methodology (AUC).
 
○ Hours 2-6
 
○ Hours 0-8
 
○ Hours 0-12
 
	
 
Key Placebo-corrected Analyses
 
The QTcF values collected on Days 2 and 4 during the following time intervals will be compared to the values on Day 1 (placebo) utilizing the trapezoidal methodology for area under the curve (AUC) calculation. Furthermore, the average AUC, which is defined as the AUC divided by the actual time span of the AUC time interval within each subject, were analyzed as post-hoc analyses. An additional time interval from hours 3 to 6 was added after examining the time course of the QTcF data.
 
○ Hours 2-6
 
○ Hours 0-8
 
○ Hours 3-6
 
	Deletion of Day 5 as the time points are not the same as Day 1; Clarification on analysis methods using AUC; Addition of new post-hoc analyses using average AUC; Addition of new post-hoc analyses using time interval of Hours 3-6.
6.4			
6.4			

## 3 Study Design

The study is a Phase 1b/2a two-part (Part 1 and Part 2) trial in male and female subjects between 19 and 60 years of age (inclusive). Part 1 is a randomized, double-blind, crossover, dose escalation, placebo-controlled study to evaluate the safety, tolerability, pharmacokinetics (PK), and pharmacodynamics (PD) of SGK-1 kinase inhibition by LQT-1213 on dofetilide-induced corrected QT (QTc) prolongation in healthy adult subjects. Part 2 is a single-blind, multiple-dose escalation safety study to evaluate the safety, tolerability, and PK of LQT-1213 in patients diagnosed with Long QT Syndrome

Type 2 (LQT2) and Long QT Syndrome Type 3 (LQT3).

#### Part 1

The design of Part 1 can be found in the protocol. The statistical plan for Part 1 was described in a separate statistical analysis plan.

#### Part 2

This will be a Phase 2a, single-blind, placebo run-in, multiple-dose safety study to evaluate the safety, tolerability, and PK of LQT-1213 in patients with LQT2 and LQT3. All patients will have a QTcF  $\geq$ 480 and  $\leq$ 560 ms. Up to 12 participants with LQT2 and up to 12 participants with LQT3 will be enrolled.

After initial remote screening by the clinical research unit (CRU), individual patients will undergo a 1-day, single blind run-in period followed by 3 dosing days of LQT-1213, administered three times a day (TID) at time 0, 8, and 16 hours on Days 2 and 3, with the final dose on Day 4 at time 0, though these time points may be adjusted based upon emerging data.

Approximately 7 days after discharge from the CRU, the Follow-up visit will be conducted remotely via telephone call. The duration of treatment for each subject in the study will be approximately 13 days, from admission on Day -1 to the telephone follow-up call. This does not include the 60-day screening period.

## 4 Cardiodynamic ECG Assessment

## 4.1 Cardiodynamic ECG Objectives and Endpoints

The objectives of the study are to:

1) Evaluate the effect of up to two separate oral doses of LQT-1213 on QTcF prolongation in patients with LQT2 and LQT3 using the QTc interval corrected for heart rate by the Fridericia's formula (QTcF).

#### 5 Statistical Methods

#### 5.1 General Methodology

For continuous variables the following descriptive statistics will be provided: number of subjects, mean, standard error of the mean (SE), standard deviation (SD), minimum (min), maximum (max), and median. For categorical variables, descriptive statistics will include the number and percentage of subjects in each category, using either the number of subjects in the treatment group or the number of subjects with non-missing values as the denominator for the percentages. All ECG data will be summarized by LQT-1213 dose groups of 16 mg and 7 mg, unless otherwise specified. Min and max values will be rounded to the precision of the original value. Means and medians will be rounded to one decimal place greater than the precision of the original value. SDs and SEs will be rounded to two decimal places greater than the precision of the original value. Typically, the confidence intervals (CIs) shall be rounded to two decimal places greater than the precision of the original value; however, due to space constraint on the printout, as well as for easier review, the CIs were rounded (post-hoc) to one decimal place greater than the precision of the original value. Percentages for summarizing categorical data will be rounded to one decimal place. P-values will be presented with four decimal places and values less than 0.0001 will be presented as <0.0001. All inferential statistical testing will be two-sided, and log-transformation of values may be performed when applicable.

In the case where a safety laboratory variable is recorded as "> x", " $\ge$  x", " $\le$  x", " $\le$  x", a value of x will be taken for summary. In listings, these data will be presented as recorded with the sign.

By-subject listings, including data at scheduled and unscheduled visits, will be sorted by treatment group, subject number, study visit and time point.

#### 5.2 Baseline

### 6 Analysis

#### 6.1 Summary Statistics Analysis

Each ECG parameter will be summarized by visit. The average of the triplicates at each time point will be presented in listings. Descriptive statistics will be used to summarize the values of the ECG variables and the corresponding changes (and percent changes) from baseline values at each time point on each of Days 1-5. The 2-sided 90%, 85%, and 80% CIs of the means will be derived based on t-test.

#### 6.2 Time-based Placebo-corrected Analysis

In this analysis, QTcF values at each time point on Days 2 and 4 will be compared to the time-matched QTcF values on Day 1 (placebo) using paired t-test, which is the same as analyzing the difference of the time-matched QTcF values using one-sample t-test.

The mean difference, median, SD, min, max, 2-sided 90%, 85%, and 80% CIs, and p-value will be reported. The null hypothesis will be rejected at significance levels of 0.1, 0.15, or 0.2 if the p-value is less than 0.1, 0.15, or 0.2, corresponding to 2-sided 90%, 85%, and 80% CIs, respectively.

Additional post-hoc analyses were conducted for all time-matched placebo-corrected analyses by pooling subjects in the LQT-1213 16 mg and 7 mg dose groups together.

The same analyses will be conducted on HR, PR and QRS.

#### 6.4 Additional Key Analysis

#### **Key Placebo-corrected Analyses**

- The QTcF values collected on Days 2 and 4 during the following time intervals, will be compared to the values on Day 1 (placebo) utilizing the trapezoidal methodology for area under the curve (AUC) calculation. Furthermore, the average AUC, which is defined as the AUC divided by the actual time span of the AUC time interval within each subject, were analyzed as post-hoc analyses. An additional time interval from hours 3 to 6 was added after examining the time course of the QTcF data.
  - o Hours 2-6
  - o Hours 0-8
  - o Hours 0-12
  - o Hours 3-6

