Section 5.4.1.2 (Pharmacodynamic Assessments – Part 2)	Continuous 12-Lead ECG Acquisition heading was removed	To reflect that safety is the primary objective
Section 5.4.3.6.2 (Physical Examinations – Part 2)	Day –1 was removed for height measurement.	Not needed as height will be captured at Screening

Section 5.7.1.3.2 (Categorical Analyses – Part 2)	Removed categorical analysis	To align with updated study design
Appendix B (Schedule of Events – Part 2) and Appendix D (PK, PD, and Meal Time Points – Part 2)	Schedule of events, PK, PD, and meal assessments updated	To align with updated study design

Amendment 6, Version 7.0 (05 December 2023):

Section # and Name	Description of Change	Brief Rationale
Section 1 (Synopsis), Study Design Part 2, Section 5.4.3.5 Part 2, and Section 5.5.5.2 Part 2	Removed sentence requiring the study blind	Thryv staff will not be blinded to Part 2 postdose ECG data prior to database lock, which aligns with the single-blind study design.
Section 1 (Synopsis), Part 2 Exclusion criteria #9 and Section 5.2.2.2. Part 2 Exclusion criteria #9	Adding allowance for sponsor and investigator approval for PR interval in participants on beta blockade	Given beta blockade can confound PR interpretation, allowance made for sponsor and investigator to review PR.
Section 8.4: Appendix D: Pharmacokinetic and Pharmacodynamic, and Meal Time Points – Part 2:	For Part 2; updated start of mealtime and updated ECG and ECG extraction times	The start time of the mealtime period on Day 1 Part 2 was updated to begin after all ECG collections are complete. Timepoints for collection of 12-lead ECGs and ECG extractions in Part 2 were updated, primarily to capture ECG information during the placebo period on Day 1.

1. Protocol Synopsis

	 
Title:	A Phase 1b/2a, 2-Part Study; Part 1: Randomized, Double-Blind, Crossover, Dose-Escalation, Placebo-Controlled Study to Evaluate the Safety, Tolerability, Pharmacokinetics, and Pharmacodynamics of SGK-1 Kinase Inhibition by LQT-1213 on Dofetilide-Induced QTc Prolongation in Healthy Adult Subjects. Part 2: Single-Blind, Multiple-Dose, Safety Study to Evaluate the Safety, Tolerability, and Pharmacokinetics of LQT-1213 in Patients Diagnosed With Type 2 or 3 Long QT Syndrome
Phase of development:	1b/2a
Investigator:	
Study site:	

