and 4, participants will begin fasting at midnight and will remain fasted until immediately after the 6-hour ECG extraction time point when a light low carbohydrate meal will be provided, which should be consumed within 30 minutes. Participants will then fast until after the 10-hour (Day 1) or 12-hour (Days 2 and 4) ECG extraction when food will be provided ad libitum until midnight. On Day 3, participants will begin fasting at midnight and will remain fasted until the 2- hour time point when food will be provided ad libitum until the 6- hour time point. Fasting will resume at the 6-hour time point until the 10-hour time point when food will be provided ad libitum until midnight. Food intake must be completed prior to the midnight fast to ensure the midnight fasting requirement is met (no food or fluid except water). On Day 5, normal food intake will begin ad libitum after the 29-hour ECG extraction. Serum potassium and magnesium will be checked each day while participants are housed (Days -1, 1, 2, 3, 4 and 5). In addition, serum potassium and magnesium may be repeated at the investigator's discretion. Potassium <3.8 mg/dL and magnesium <1.8 mg/dL will result in additional electrolyte supplementation. Electrolyte supplementation can be administered 12-18 hours after the morning dose of LQT-1213.

Safety assessments will include AEs, clinical laboratory test results, vital signs measurements, continuous telemetry ECG monitoring, and safety 12-lead ECG findings. Bedside safety 12-lead ECGs will be collected by the CRU staff and reviewed by the investigator. The safety ECG data, including all time points, will be recorded on the eCRF, and be used for evaluating general safety of the participants with LQT2 or LQT3 during study and for evaluation of an AE. All ECG sent to will be stored for possible future analysis.

The dosing, meal timing, and PK and ECG time points and extractions may be modified based on emerging data.

Study drug, dosage, and	Part 1:
route of administration:	 LQT-1213 low, mid, and high (not to exceed 0.747 mg/kg TID, daily dose 2.24 mg/kg/day) doses TID (at time 0, immediately after the 7.75-hour ECG extraction time point, and at 17 hours) for oral suspension (Days 3-8; only 1 dose will be administered on Day 8) Part 2: LQT-1213: TID (at time 0, 8, and 16 hours) on Days 2 and 3 and a single morning dose on Day 4 (last dose on Day 4 is the am dose). The dose will not exceed daily dose 2.24 mg/kg/day for oral suspension

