On Day -1, there are no fasting requirements with the exception of an overnight 6-hour fast for clinical laboratory collections. On Days 1, 2, and 4, participants will begin fasting at midnight and will remain fasted until immediately after the 6-hour ECG extraction time point when a light low carbohydrate meal will be provided, which should be consumed within 30 minutes. Participants will then fast until after the 10-hour (Day 1) or 12-hour (Days 2 and 4) ECG extraction when food will be provided ad libitum until midnight. On Day 3, participants will begin fasting at midnight and will remain fasted until the 2- hour time point when food will be provided ad libitum until the 6- hour time point. Fasting will resume at the 6-hour time point until the 10-hour time point when food will be provided ad libitum until midnight. Food intake must be completed prior to the midnight fast to ensure the midnight fasting requirement is met (no food or fluid except water). On Day 5, normal food intake will begin ad libitum after the 29-hour ECG extraction. Participants will not be allowed to sleep during the ECG resting or collection times. Participants will be supine, with legs uncrossed, arms at the side, remain quiet, and refrain from laughing and talking for 10 minutes before, during, and approximately 5 minutes after each scheduled ECG extraction time point for motion-free recordings. Staff will work quietly during this same period, keeping conversation to a minimum.

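### The Hours 0-12 QTcF AUC contrast in SAP 6.4 is not like-for-like after hour 10: Day 1 hours 10-12 are either unsampled or not meal-matched to Days 2 and 4

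*SAP*

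**What the plan says.** SAP 6.4 (Key Placebo-corrected Analyses) states that QTcF values on Days 2 and 4 "will be compared to the values on Day 1 (placebo) utilizing the trapezoidal methodology for area under the curve (AUC) calculation". Its body lists four windows: Hours 2-6, 0-8, 0-12 and 3-6. It adds an average AUC, defined as "the AUC divided by the actual time span of the AUC time interval within each subject, were analyzed as post-hoc analyses". SAP 6.2 compares time-matched values on Days 2 and 4 with Day 1 by paired t-test, for QTcF and also for HR, PR and QRS.

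Protocol 5.5.8.2 sets the meals. On Days 1, 2 and 4 participants fast from midnight and "will remain fasted until immediately after the 6-hour ECG extraction time point when a light low carbohydrate meal will be provided". After that the days separate: "Participants will then fast until after the 10-hour (Day 1) or 12-hour (Days 2 and 4) ECG extraction when food will be provided". The Part 2 study design in the Protocol Synopsis gives the same rule.

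The ECG time points are in Protocol Appendix D, whose table is not in the text available for this review. SAP Section 2 says that "this analysis utilizes concomitantly recorded 12 lead ECGs", although Holter recordings were also made.

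**The concern.** An AUC contrast with placebo is interpretable when both days cover the same hours under the same conditions. Days 1, 2 and 4 share the fast to hour 6 and the light meal, so they are matched up to hour 10. From hour 10 to hour 12, Day 1 participants may eat freely, while on Days 2 and 4 they are still fasting. Either Day 1 has no ECG in those two hours, and the 0-12 window has no placebo data for its last sixth, or it has one that follows food on one side of the comparison only.

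The SAP already recognises the principle. Its change table explains that Day 5 was removed from Sections 6.2 and 6.4 because its time points differ from those of Day 1. The visible text does not apply that reasoning to hours 10-12.

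At stake is one of the key late-window summaries, and the only listed window that runs past the 8-hour dose on Day 2. Any hour-12 contrast in Section 6.2 has the same mismatch.

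**Working it through.** The plan gives no power, error rate or effect size for this Part 2 contrast, so there is no figure to reproduce. The check has two steps.

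**Step 1: is Day 1 sampled after hour 10?** The visible evidence points both ways.
- Against sampling: the Amendment 6 entry in the protocol's summary of changes says "The start time of the mealtime period on Day 1 Part 2 was updated to begin after all ECG collections are complete". With food opening after the 10-hour extraction, that suggests no 12-hour ECG on Day 1.
- For sampling: the same entry says ECG times "were updated, primarily to capture ECG information during the placebo period on Day 1". The SAP also analyses 12-lead ECGs rather than Holter extractions, so the 10-hour extraction does not by itself date the last analysed ECG.

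Both cases are therefore sized.

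**Step 2: size.** Inputs from the documents are the QTcF range of 480-560 ms (Part 2 inclusion criterion 7), the 12-hour window, and the 10-hour and 12-hour food times. The late-minus-early difference and the food effect are assumptions, each taken as 2-10 ms. The documents give neither.

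*Case 1: Day 1 ends at 10 h, Days 2 and 4 run to 12 h, no drug effect.*
- Average AUC. Let A be mean QTcF over hours 0-10 and B the mean over hours 10-12. The 12-hour average is (10A + 2B)/12. Subtracting the Day 1 average A leaves (2/12) × (B − A). For B − A of 2, 5 and 10 ms this is 0.3, 0.8 and 1.7 ms.
- Raw AUC, only if each day is run to its own last point. On a flat profile the extra area is 2 h × 480 ms = 960 ms·h to 2 h × 560 ms = 1120 ms·h. For scale, a constant 10 ms effect over 12 h is 10 × 12 = 120 ms·h.

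*Case 2: Day 1 has a 10-hour ECG and a 12-hour ECG after food.*
- If hour 12 is the only point after hour 10, the trapezoid gives the food effect a weight of ½ × 2 h = 1.0 h. The shift in average AUC is (1.0/12) × 2 to 10 ms = 0.2 to 0.8 ms.
- If hour 11 is also recorded and carries the same effect, the weight is 0.5 + 1.0 = 1.5 h. The shift is (1.5/12) × 2 to 10 ms = 0.3 to 1.3 ms.
- A Section 6.2 contrast at hour 12 takes the full assumed 2-10 ms for QTcF.

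*Windows 2-6, 3-6 and 0-8:* the food rules are the same on all three days up to hour 10, so this difference contributes zero.

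**The case against.** The strongest reply is that the point depends on an unseen table. Appendix D would show whether Day 1 has a 12-hour ECG. SAP 5.2, 6.3 and parts of 6.4 have no visible content, and a handling rule may sit there. The protocol also lets meal and ECG times change with emerging data, so the written rule need not be what was done. The SAP authors examined Day 1 matching when they dropped Day 5 and kept Days 2 and 4, which weighs against an overlooked gap. All of this stands. It limits what can be said about which case applies, but the 0-12 contrast is not like-for-like in either case on the text as written.

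Four stronger readings are tempting, and the documents do not support them.
- A reader might infer that the raw AUC carries a false difference of about 1000 ms·h. That requires a Day 1 area computed over 10 h under a 0-12 label. No section says this was done, and an error of that size would be obvious.
- A reader might infer that food lengthens placebo QTcF and so favours the drug, since Protocol 3.1 links insulin to SGK-1 and SGK-1 to longer action potentials. The same section says baseline SGK-1 activity in cardiomyocytes is low. Nothing in the documents gives the size or sign of a meal effect on QTcF within two hours.
- A reader might treat the SAP change table as a contradiction, because its amended column omits Hours 0-12 while the body lists it. A change log may differ from the current text, so this is noted and not counted as an error.
- A reader might conclude that raw AUC should be demoted in favour of average AUC. That would be a preference for a post-hoc measure and does not follow from the mismatch.

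**Conclusion.** The concern holds, and it is minor. As written, the last two hours of the 0-12 contrast do not compare like with like, whichever way Appendix D reads. Average AUC, which is post hoc, removes the span artefact on a flat profile. It does not restrict to time points present on both days and does not deal with food.

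The residual in average AUC is 0.3-1.7 ms if Day 1 stops at 10 h, or about 0.2-1.3 ms if Day 1 has a 12-hour ECG after food. Both ranges rest on assumed 2-10 ms inputs and scale directly with them. A hour-12 contrast in Section 6.2, if one exists, takes the full assumed amount. Raw AUC over unequal spans would simply not be comparable. The other three windows are unaffected, and Part 2's primary objective is safety and tolerability, so no primary conclusion rests on this.

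**What to change.** 1. Reconcile Hours 0-12 in SAP 6.4 with the Day 1, 2 and 4 ECG times in Appendix D.
2. State that each AUC contrast, raw and average, is computed within subject using only nominal time points with a value on both Day 1 and the comparison day. If removed text already holds such a rule, refer to it in 6.4.
3. Label the late window by its true common span: 0-10 h if the 10-hour 12-lead ECG exists on all three days, otherwise rely on 0-8 h.
4. The common-point rule does not cure a Day 1 hour-12 value taken after food. Keep any 0-12 AUC, and any hour-12 contrast in Section 6.2 (QTcF, HR, PR, QRS), visible but flagged as not meal-matched, giving the 10-hour and 12-hour food times.
5. Declare the change as made on schedule grounds after data were seen. The SAP change table shows Hours 0-12 in the original text, so it should not disappear.

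The cost is SAP wording and a re-run; no change to the meal schedule is proposed. The downside is that hours 10-12 then have no like-for-like placebo contrast. If the drug effect in those hours differs from the earlier effect by an assumed 5 ms, a 0-10 h average differs from a 0-12 h one by (2/12) × 5 = 0.8 ms.
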